#### 8.3 Reporting Procedures for All SAEs/ SADEs/ UADEs

All SAE/SADE/UADEs need to be reported to the sponsor/legal representative and manufacture and CUH R&D immediately; regardless of relationship to the device.

All reporting to CUH R&D should give as much information about the incident as possible, and should be signed by the PI or Co-investigator.

The CUH R&D Department will undertake an initial review of the information. Events will be followed up until resolution, any appropriate further information will be sent by the research team in a timely manner.

Reporting to the MHRA will be done in liaison with the Chief Investigator and the Manufacturer.

The Manufacturer has a legal obligation to report all events that need to be reported to the Nominated Competent Authority immediately (without any unjustifiable delay) after a link is established between the event and the device, but no more than:

- ♣ 2 days following the awareness of the event for Serious Public Health Threat.
- 4 10 days following awareness of the event for Death or unanticipated serious deterioration in health.

CONFIDENTIAL

Formatted: Superscript, Not Highlight

Formatted: Not Highlight

Version 2 April 12th 2021

30 days following the awareness of the event for all other event meeting the SAE criteria.

#### 8.4: Annual Reports

In addition to the above reporting the Chief Investigator will submit once a year, throughout the trial, or on request a progress/safety report to the REC and R&D.

#### 9 STATISTICS

#### 9.1 Description of Statistical Methods/ Sample size

#### 9.1.1 Analysis of Primary Endpoint

This is a pilot study to test KYMIRA's device on human subjects for the first time, with the primary outcome of interest being its effectiveness in detecting fetal movements, as identified by the operator scanning, compared with those detected by the pregnant women.

The analysis of the primary endpoint will therefore be a comparison of the proportion of movements, as identified by the scan operator, that are successfully detected by the wearable device compared with the proportion detected by the pregnant women, at each of weeks 32, 34, 36, and 38 of pregnancy separately.

The data to be analysed are the binary (Yes/No) outcomes for the device and the mother indicating whether each of the scan operator movements was successfully identified. There will be an outcome for the device and the mother (Yes/No, i.e., Detected/Not detected) for the same scan operator-identified movement. The data are therefore paired and a McNemar's test of paired proportions will be conducted to detect a difference in the proportions of movements detected by the device compared with the mother, if such a difference exists.

The same analysis will be repeated for the week 32, 34, 36 and 38 visit movements separately. The movements at a particular visit (either week 32, 34, 36 or 38) will be collated across the pregnant women for analysis. The repeated foetal movements for a given pregnant woman during a particular scan will be treated as independent.

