## 7.2 Maintenance and storage of device

The device will be in two parts. The fabric wearable part and a separate recording box with its own low power supply and data recording abilities. The fabric part will be new for each patient. The fabric part will be stored in a plastic sealed folder in the research room. Labelled with patients study number, in between scans. The plastic box part will be Clinicel wiped in between each patient. The device will be maintained by Kymira but training will be given to the staff at CUH.

Formatted: Superscript, Not Highlight

Formatted: Not Highlight

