## 9.1.1.1 Sample Size Determination

Previous studies that compared the number of fetal movements observed by ultrasound and those perceived by mothers during the 3rd trimester (Brown R, 2016) (Hertogs K, 1979) found the later to be highly varied; with different studies reporting different average fractions in the range of 0.16 to 0.44 (Hertogs K, 1979). Hence, we calculated the sample size for an

CONFIDENTIAL

Formatted: Not Highlight

Formatted: Superscript, Not Highlight

Formatted: Not Highlight

Page 17 of 29

Version 2 April 12th 2021

assumed sensitivity rate of 44% for the pregnant mothers, corresponding with the most conservative estimate, i.e., to ensure adequate power. Based on the initial simulation tests of our device, we expect it to detect 0.8 to 0.9 fraction of the fetal movements. Allowing for a potentially lower detection rate in clinical practice, we assumed a sensitivity rate of 60% for the wearable device, again corresponding a larger sample size to ensure sufficient power.

For a single visit (week 32, 34, 36 or 38), based on a two-sided McNemar's test with a 5% significance level and 90% power, 395 movements are required (according to Lachenbruch (1992) (Lachenbruch, 1992) and based on the minimum estimate of the phi correlation r). Each pregnant woman is expected to have a minimum of around 10 foetal movements per 20 minute scan, as detected by the sonographer, therefore (rounding up) approximately 40 subjects are required for the study analysis.

In addition, an independent "training" subset of the data are required for calibrating the device. It is estimated that 3 subjects will be required for this purpose (i.e., approximately 30 movements), taking the number of subjects in the study to 43. Allowing for a drop-out rate of approximately 20%, a final sample size of 54 subjects (again rounding up) are estimated to be required for recruitment into the study. As the sample size required is based upon the number of foetal movements, if a different number of movements per mother is observed than assumed, the number of subjects recruited will be amended to ensure an appropriate total number of movements available for analysis.

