#### 9.1.3 Other Analyses

In addition to the analysis of the primary endpoint outlined above, an additional exploratory analysis may be conducted, pooling the data across visits and comparing the overall proportions of movements detected by the device compared with the mothers.

Summary statistics will be provided for subject demographics, medical history, and baseline measures.

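### The primary McNemar test treats a woman's repeated movements as independent, so any within-woman correlation of the device-minus-mother difference inflates its type I error and makes the stated power conditional

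*Protocol*

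**What the plan says.** The unit of analysis in section 9.1.1 is the movement seen by the scan operator, scored as detected or not by the device and by the mother. At each visit the movements "will be collated across the pregnant women for analysis", and "a McNemar's test of paired proportions will be conducted to detect a difference in the proportions of movements detected by the device", set against that for the mother. The section then fixes the dependence structure: "The repeated foetal movements for a given pregnant woman during a particular scan will be treated as independent".

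Section 9.1.2 makes the same assumption for positive predictive value, using a z-test of independent proportions.

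Section 9.1.1.1 sizes the study in movements: "based on a two-sided McNemar's test with a 5% significance level and 90% power, 395 movements are required" per visit, with an "assumed sensitivity rate of 44% for the pregnant mothers", 60% for the device and the minimum phi correlation between the two. It divides by about 10 movements per scan to reach 40 women, adds 3 for training and allows 20% drop-out to reach 54. No design effect is applied. If movements per woman differ from 10, recruitment is changed to hold the total number of movements.

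The protocol gives no cluster-adjusted or woman-level analysis and no reason for assuming independence.

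**The concern.** The protocol's own design points away from independence.

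- On the device side, section 7.2 says "The fabric part will be new for each patient", so the fit and placement of one fabric element are common to all of a woman's movements in a scan.
- On the mother's side, one person presses the button throughout, and section 4 says that some women find movements hard to perceive.
- Section 6.2.1 records a further event when a movement persists, so one continuing movement can supply several rows.

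McNemar's variance counts every row as a separate piece of evidence. If a woman's rows tend to favour the device or the mother together, the variance is too small. The claim that the device detects more movements than the mother, or fewer, would then be made too easily. The number of women needed for a valid test would also be understated.

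**Working it through.** **Inputs from section 9.1.1.1.** Mother 0.44, device 0.60, two-sided 5%, 90% power, minimum phi, 10 movements per woman, 40 women (400 movements).

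**Reproducing 395.** The smallest possible joint detection is 0.44 + 0.60 − 1 = 0.04. The discordant cells are 0.60 − 0.04 = 0.56 and 0.44 − 0.04 = 0.40. Discordance D = 0.96, difference d = 0.16, phi = −0.92.

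n = (1.96 + 1.2816)² × D / d² = 10.508 × 0.96 / 0.0256 = 394.03, rounded up to 395. Then 395/10 = 39.5, so 40 women, and (40 + 3)/0.8 = 53.75, so 54. The plan's figures reproduce, with a within-woman correlation of zero.

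**Adding clustering.** The relevant ICC is that of the device-minus-mother difference. The protocol gives none, so 0.02 to 0.20 is an assumption.

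- Design effect: DE = 1 + (10 − 1) × ICC
- Effective movements: n_eff = 400 / DE
- True type I error of the planned test: 2 × [1 − Φ(1.96 / √DE)]
- Power of a valid 5% test: Φ[(d√n_eff − 1.96√D) / √(D − d²)]

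Example, ICC 0.10: DE = 1.9 and n_eff = 210.5. Type I error = 2 × [1 − Φ(1.422)] = 0.155. Power = Φ[(0.16 × 14.51 − 1.96 × 0.980) / 0.967] = Φ(0.415) = 0.66.

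For phi = 0, joint detection is 0.44 × 0.60 = 0.264 and D = 1.04 − 2 × 0.264 = 0.512.

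| ICC (assumed) | DE | True type I error | Power, minimum phi (D = 0.96) | Power, phi = 0 (D = 0.512) |
|---|---|---|---|---|
| 0 | 1.00 | 5% | 91% | >99% |
| 0.02 | 1.18 | 7% | 86% | 99% |
| 0.05 | 1.45 | 10% | 78% | 96% |
| 0.10 | 1.90 | 16% | 66% | 91% |
| 0.20 | 2.80 | 24% | 50% | 77% |

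**Simulation check.** 10,000 replicates of 40 women × 10 movements were run, with both sensitivities at 0.52 and separate beta-distributed woman effects for mother and device. The ordinary McNemar test rejected in 10.8%, 15.8% and 24.7% at ICC 0.05, 0.10 and 0.20. A woman-clustered version rejected in 4.9%, 4.9% and 5.1%. When device and mother shared one identical woman effect, the ordinary test rejected in 4.7%.

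**The re-sizing rule.** With 20 movements per woman, holding the total near 400 would accept 20 women. At ICC 0.10, DE = 1 + 19 × 0.10 = 2.9, n_eff = 400/2.9 = 138, and power at minimum phi is about 48%, against 66% with 40 women × 10 movements.

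**The case against.** Several points on the other side are sound.

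- **The ICC is unknown.** Only correlation in the difference matters. A woman effect common to device and mother, such as one due to her abdomen alone, would cancel if it acted equally on both. The type I error figures are therefore a conditional range. But a mother's perception and the fit of her fabric element are separate sources, and nothing in the protocol suggests that they cancel.
- **The sizing is cautious.** It takes 44% from the top of a 0.16 to 0.44 range, 60% although 0.8 to 0.9 is expected, and the least favourable phi. A reader might infer that 90% power fails as soon as the ICC exceeds zero. The documents do not support that: at phi = 0 power is still about 91% at ICC 0.10. With 0.70 against 0.44 at minimum phi (joint detection 0.14, D = 0.86, d = 0.26), the same formula gives about 93% at ICC 0.20. This margin protects power only; it has no bearing on type I error.
- **Highly varied perception.** A reader might take that remark in section 9.1.1.1 as evidence of variation between women. It describes averages from different studies, so it is not used here.
- **Intervals.** A reader might add that planned intervals will be too narrow. The protocol plans none for the primary difference. Its only interval is for acceptability, with one response per woman.
- **The pooled analysis.** Section 9.1.3 mentions "pooling the data across visits and comparing the overall proportions of movements detected by the device" with that for the mothers, but as exploratory and optional, with no test named. It is a place to carry the fix through, not a separate error.
- **Pilot status.** The study is a first test in human subjects and the assumption is disclosed. The protocol still fixes a powered two-sided 5% test as its primary analysis, so the test should hold its level.

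**Conclusion.** Wrong as written. The independence rule is fixed in the protocol, conflicts with how the data arise, and is not offset by any other planned analysis. With 40 women × 10 movements and an assumed ICC of the difference between 0.02 and 0.20, the nominal 5% primary test has a true type I error of about 7% to 24%.

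The power conclusion is weaker and conditional. The 395 movements are correct arithmetic for zero ICC. Under the plan's own inputs, a valid test with 40 women has about 86% down to 50% power over that range. At phi = 0 it has about 99% down to 77%, and larger true differences give more. The documents therefore do not show that 40 women are too few; they show that 90% is not assured.

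The same independence statement in section 9.1.2 needs correcting, but its effect on the positive predictive value comparison was not quantified.

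**What to change.** - **Section 9.1.1:** replace the independence statement and plain McNemar test with a clustered McNemar test (Obuchowski or Durkalski), or GEE with robust variance and woman as the cluster. Report the difference in sensitivity with a cluster-robust 95% confidence interval.
- **Section 9.1.2:** replace the z-test of independent proportions with a woman-clustered comparison of the two positive predictive values.
- **Section 9.1.3:** if the pooled analysis is done, keep woman as the cluster across visits.
- **Section 9.1.1.1:** give the power of 40 women over a stated range of ICC and phi, and make the re-sizing rule take account of the number of women as well as the total movements.

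**Cost.** The analysis changes need only wording and standard software, and data collection is unchanged. The stated power becomes conditional and may fall clearly below 90% under the worst-case phi. Holding 90% there would need 395 × DE / 10 women analysed: 58, 76 or 111 at ICC 0.05, 0.10 or 0.20. The sponsor can keep 40 women if it accepts and states the conditional power.

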## 9.1.1.1 Sample Size Determination

Previous studies that compared the number of fetal movements observed by ultrasound and those perceived by mothers during the 3rd trimester (Brown R, 2016) (Hertogs K, 1979) found the later to be highly varied; with different studies reporting different average fractions in the range of 0.16 to 0.44 (Hertogs K, 1979). Hence, we calculated the sample size for an

CONFIDENTIAL

Formatted: Not Highlight

Formatted: Superscript, Not Highlight

Formatted: Not Highlight

Page 17 of 29

Version 2 April 12th 2021

assumed sensitivity rate of 44% for the pregnant mothers, corresponding with the most conservative estimate, i.e., to ensure adequate power. Based on the initial simulation tests of our device, we expect it to detect 0.8 to 0.9 fraction of the fetal movements. Allowing for a potentially lower detection rate in clinical practice, we assumed a sensitivity rate of 60% for the wearable device, again corresponding a larger sample size to ensure sufficient power.

For a single visit (week 32, 34, 36 or 38), based on a two-sided McNemar's test with a 5% significance level and 90% power, 395 movements are required (according to Lachenbruch (1992) (Lachenbruch, 1992) and based on the minimum estimate of the phi correlation r). Each pregnant woman is expected to have a minimum of around 10 foetal movements per 20 minute scan, as detected by the sonographer, therefore (rounding up) approximately 40 subjects are required for the study analysis.

In addition, an independent "training" subset of the data are required for calibrating the device. It is estimated that 3 subjects will be required for this purpose (i.e., approximately 30 movements), taking the number of subjects in the study to 43. Allowing for a drop-out rate of approximately 20%, a final sample size of 54 subjects (again rounding up) are estimated to be required for recruitment into the study. As the sample size required is based upon the number of foetal movements, if a different number of movements per mother is observed than assumed, the number of subjects recruited will be amended to ensure an appropriate total number of movements available for analysis.

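### The recruitment rule in 9.1.1.1 tracks only the movement total and sets no minimum number of women, so it permits a cut in the independent units while the target of 395 movements still looks met

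*Protocol*

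**What the plan says.** Section 9.1.1.1 of the protocol works in movements, not women. For each visit it states that for a "two-sided McNemar's test with a 5% significance level and 90% power, 395 movements are required". This rests on an "assumed sensitivity rate of 44% for the pregnant mothers", on the statement "we assumed a sensitivity rate of 60% for the wearable device", and on a pair correlation "based on the minimum estimate of the phi correlation r".

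Movements are turned into women through one assumption: "Each pregnant woman is expected to have a minimum of around 10 foetal movements per 20 minute scan". From that, "approximately 40 subjects are required for the study analysis". Three training women and a drop-out allowance of about 20% bring recruitment to 54.

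The closing sentence makes the number of women adjustable: "if a different number of movements per mother is observed than assumed", then "the number of subjects recruited will be amended to ensure an appropriate total number of movements available for analysis". It gives no direction, no minimum number of women and no within-woman correlation.

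Three other places bear on this:
- Section 6.2.1 counts any trunk or limb movement and logs a further event when a movement persists.
- Sections 6.1 and 7.2 give each woman her own fabric element.
- Sections 9.1.1 and 9.1.2 treat all movements of a woman within a scan as independent.

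**The concern.** The rule controls the wrong unit. Section 4 of the protocol says that some women find movements hard to perceive, so maternal detection differs between women. Each woman wears her own garment, so device detection may differ too. Movements within one woman are therefore likely to be correlated, and the effective number of movements cannot exceed the number of women divided by the ICC, however many events are logged.

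If counts run above 10 per scan, the rule permits fewer women while the total still reaches 395. The report could then claim the planned 90% power with much less information behind it. The acceptability proportion in 9.1.2 is counted per woman, so extra movements do nothing for it. Women who were never recruited cannot be recovered at the analysis stage.

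**Working it through.** **Inputs from 9.1.1.1.** Sensitivities 0.60 (device) and 0.44 (mothers), so d = 0.16; two-sided 5%; 90% power; minimum phi; 10 movements per scan.

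**Assumption.** The ICC of the paired device-minus-mother outcome is not in the protocol. I use 0.02, 0.05 and 0.10, and also show 0.

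**1. The plan's own figures.** Minimum phi means the smallest possible joint detection, 0.44 + 0.60 − 1 = 0.04. The discordant share is ψ = 0.60 + 0.44 − 2 × 0.04 = 0.96. Then (1.960 + 1.282)² × 0.96 / 0.16² = 394.03, rounded up to 395. Next, 395 / 10 = 39.5, so 40 women, and (40 + 3) / 0.80 = 53.75, so 54. The stated arithmetic is correct under independence.

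**2. What the rule permits.** With about 400 movements as the target, 20 events per scan needs 400 / 20 = 20 women, and 40 events needs 400 / 40 = 10 women.

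**3. Effective size and power.** For K women with m movements each:
- design effect = 1 + (m − 1) × ICC
- n_eff = K × m / design effect
- power = Φ{(0.16 √n_eff − 1.96 √ψ) / √(ψ − 0.16²)}

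This is a normal approximation to a test that allows for clustering. Worked case, 10 women × 40 movements at ICC 0.10: design effect 1 + 39 × 0.10 = 4.9; n_eff = 400 / 4.9 = 81.6; power = Φ{(1.445 − 1.920) / 0.967} = Φ(−0.49) = 31%.

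Power at the plan's minimum phi (ψ = 0.96):

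| Women × movements | ICC 0 | 0.02 | 0.05 | 0.10 |
|---|---|---|---|---|
| 40 × 10 (as planned) | 91% | 86% | 78% | 66% |
| 20 × 20 (rule followed) | 91% | 80% | 65% | 48% |
| 40 × 20 (women kept) | about 100% | 98% | 91% | 78% |
| 10 × 40 (rule followed) | 91% | 69% | 48% | 31% |
| 40 × 40 (women kept) | about 100% | about 100% | 97% | 84% |

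With few women the approximation is somewhat generous. In a simulation using a t-test on woman-level differences, 10 × 40 gave about 40% and 27% at ICC 0.05 and 0.10.

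**4. Less pessimistic pairing.** With phi = 0, ψ = 0.60 × 0.56 + 0.40 × 0.44 = 0.512. For 10 × 40, power is then about 92, 75 and 52% at the three ICCs. The loss is smaller but still present.

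**5. Acceptability.** At an assumed 80% agreement, the 95% half-width is 1.96 √(0.16 / K): about 12 points for 40 women, 18 for 20 and 25 for 10, with training women left out throughout.

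**6. Type I error.** For the planned McNemar test the error depends on the design effect, and so on m and the ICC, not on K. At m = 40 and ICC 0.10 it is 2 × {1 − Φ(1.96 / √4.9)} = about 38% with 10 women and with 40 women alike.

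**The case against.** The other side has a good deal to say.

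- **A cut is not prescribed.** The sentence can be read as protection against too few movements, and it does not say that recruitment falls in proportion. No count above about 10 is forecast anywhere, and that 10 may already include repeat events. This stands: a reduction is permitted and plausible, not certain.
- **Practical brakes exist.** The target applies to each of four visits, so the visit with the fewest movements governs. Week-38 counts arrive about six weeks after a woman's first scan, within a June to December study period. Many women would be enrolled before a cut could be justified. This lowers the likelihood but puts no floor in the text.
- **The design inputs are pessimistic.** The protocol expects the device to detect 0.8 to 0.9 of movements. At 0.80 against 0.44, the same formula gives about 97% power even for 10 × 40 at ICC 0.10 and minimum phi. Still, 60% is the value on which the plan bases its 90%.
- **It is a pilot.** That is so, but the protocol claims 90% power for a formal test.

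Two stronger readings should be resisted. A reader might infer that the study will shrink to a handful of women; about 5 women would need about 80 events in a 20-minute scan (395 / 5 = 79), which nothing in the protocol suggests. A reader might also blame the rule for the 38% false-positive rate. Step 6 shows that this rate is the same with 10 or 40 women at that count. It comes from the independence assumption in 9.1.1.

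**Conclusion.** The concern holds in limited form. Section 9.1.1.1 lets the number of women move either way to reach a movement total, with no minimum. If counts exceed 10 per scan and the rule is used to recruit fewer women, power falls well below what the planned 40 women would give: by about 18 to 30 percentage points for 20 women at 20 movements, and by about 31 to 53 points for 10 women at 40, over ICCs of 0.02 to 0.10 at the plan's phi. The acceptability interval widens as well.

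The size rests on an ICC that the protocol does not give, on 60% against 44%, and on minimum phi. At an ICC of zero, power stays at the planned level of about 91% however few women supply the movements. The planned figures of 395, 40 and 54 are not in dispute.

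**What to change.** Replace the last sentence of 9.1.1.1 with:

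> At least 40 evaluable women, excluding the training women, will be studied whatever the number of movements per woman; recruitment may be increased, but not reduced, if fewer movements than assumed are observed.

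The cost is one sentence. The floor equals the number already planned, so nothing is added to the 54. The only loss is the option to recruit fewer women.

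The floor has limits. It does not by itself secure 90% power when the ICC is above zero: 40 women × 10 movements at ICC 0.10 gives about 66% at the plan's phi. Nor does it correct the type I error of the planned McNemar test, which needs an analysis that allows for clustering by woman and should be handled as a separate point.
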